**TABLE 1. Schedule of Procedures**

Visit Assessment*	Visit 1 (14-28 days)	Visit 2 ( 1-10 days after Visit 1)
Informed Consent (Minor)	X	
Recumbent Length	X	X
Weight	X	X
PEA POD	X	
DXA	X	
MRI	X	X
Questionnaires#	X	
#Completed by a parent or legal guardian that signs the study informed consent and HIPAA authorization and accompanies the infant to the visit		

### 8.1. Visit 1

The parent/guardian and infant will be escorted to the Maternal and Infant Phenotyping Room for informed consenting. The minor informed consent form and HIPAA authorization will be provided for review and completion after all questions are answered. After obtaining written parental informed consent for participation, the following procedures will be performed: infant weight, recumbent length, body composition by PEA POD, DXA and MRI. Questionnaires will be administered to a parent/guardian who attends the visit. The DXA and MRI procedures will be completed while the infant is sleeping. The order of the procedures at the visit will be conducted in a manner that is most respectful to the schedule and temperament of the infant. For example, if the infant arrives at Pennington Biomedical and is soundly sleeping, once the parents/legal guardians sign the informed consent, the infant may proceed directly to imaging for DXA and MRI. Visit 2 will be scheduled to occur 1-10 days later.

### 8.2. Visit 2

The following procedures will be performed: infant weight, recumbent length, and MRI. The order of the procedures at the visit will be conducted in a manner that is most respectful to the schedule and temperament of the infant. Infants will be fed and calmed before preparation for MRI. The MRI procedures will be completed while the infant is sleeping.

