### 9.2. Infant Body Composition

#### 9.2.1. PEA POD

Body composition will be assessed in infants weighing less than or equal to 8 kilograms with air displacement plethysmography (Life Measurement Inc, Concord, CA), as previously described [35, 36] at Visit 1. The infant will be placed in a special chamber called a PEA POD (pictured). The infant will lay naked in the supine position on a flat tray that slides into a transparent plastic chamber. The amount of volume (space) occupied by the infant will be measured. The staff will be able to monitor the child during the test through the transparent top.

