#### 9.3.1.2. Procedure

Magnetic resonance imaging (MRI) will be performed using a 3.0 T scanner (General Electric Healthcare, Signa Exite HDxT, Chicago, IL). Preferably after feeding, clothes will be removed and diaper changed. Then, infants will be swaddled in a blanket. Infants will be soothed to the point of sleep, and, once soundly asleep, the infant will be moved to the MRI scanner room to finish preparation and testing. Disposable neonatal noise guards (Latex-free, Newmatic Medical) specifically designed for infants in MRI environments will be applied to the infants' ears

for noise shielding. In preparation for MRI positioning, the infant will be placed in scanner with padding positioned around the infant to provide a comforting swaddle without allowing movement during the test. The pulse oximeter will be applied to the foot, and heart rate and oxygen saturation will be continuously measured throughout the test. In addition, a study staff member who is trained in neonatal BLS will be present at all times during the preparation and will remain next to the scanner during testing. Scan time will be about 10 minutes, but there is a possibility of rescanning if the infant wakes, the technician detects too much movement, or there was misplacement of the infant on the scanning table. If the infant seems to be waking through movement detection, noises, or increased heart rate from the pulse oximeter, scanning will be interrupted so that the baby can be settled and scanning can resume. In addition, the test may be stopped if the baby is not resting quietly and appears uncomfortable or distressed by the procedure.

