### **11.2. Data Analysis Plan**

As noted in Section 2. Aims, the primary aim is to develop techniques for measuring whole body adiposity (fat mass) and brown adipose tissue in infant subjects. We intend on understanding the repeat test accuracy of the measurement of infant BAT by calculating % BAT and comparing the test-retest reliability between Visit 1 and Visit 2 measurement within various equivalency intervals (e.g. within 15%, 10%, 5%). The coefficient of variation for the BAT measurement will be computed from the two measures performed under the same conditions 1 to 10 days apart.

% BAT will be calculated: 
$$\% BAT = \frac{BAT\ mass\ (by\ MRI)}{FAT\ mass\ (by\ DXA)}$$

Depending on the characteristics of the recruited cohort, exploratory analyses maybe undertaken to determine differences in measures between boys and girls, if energy expenditure is different on the account of maternal BMI, birth weight, breast milk versus formula-fed infants.

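### The plan treats the two BAT scans as done under the same conditions, but the visit procedures do not secure this, so the CV may carry a preparation component tied to visit

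*Combined protocol and SAP*

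**What the plan says.** Aim 3 (Section 2) is to evaluate the accuracy and precision of the BAT measurement from two visits, together with feasibility. Section 11.2 turns this into a CV that "will be computed from the two measures performed under the same conditions 1 to 10 days apart", and a comparison of Visit 1 with Visit 2 against example intervals of 15%, 10% and 5%. Section 11.1 gives no formal power calculation and intends the data for sample-size estimates in later projects.

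Three places describe feeding before the scan:

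- Section 8.1 (Visit 1) has no feeding step. For an infant who arrives soundly asleep, once consent is signed, "the infant may proceed directly to imaging for DXA and MRI".
- Section 8.2 (Visit 2): "Infants will be fed and calmed before preparation for MRI".
- Section 9.3.1.2 (every MRI): "Preferably after feeding, clothes will be removed and diaper changed".

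The visits also differ in content. Visit 1 comprises "infant weight, recumbent length, body composition by PEA POD, DXA and MRI", plus parent questionnaires. Visit 2 comprises "infant weight, recumbent length, and MRI". For the PEA POD test, Section 9.2.1 states: "The infant will lay naked in the supine position on a flat tray". For DXA the infant wears only a diaper and is swaddled (9.2.2.2). At both visits the order of procedures follows the infant's schedule and temperament.

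**The concern.** Identical conditions at the two scans are what would let the CV be read as the repeatability of the MRI method. The plan states that property as a fact, but the procedures allow the two scans of one infant to follow different preparation: unfed at Visit 1 and fed at Visit 2, or after PEA POD and DXA at Visit 1 and after neither at Visit 2.

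If preparation affects the MRI value, the effect would be counted as measurement error. Visit 1 always comes first, so a preparation difference between visits would also be confounded with growth over the 1 to 10 day gap. The documents describe no record of time since feeding, or of procedures already done, at each scan. Without such a record the two sources could not be examined afterwards. At stake is the description and usefulness of the study's only precision figure, which is meant to inform the size of future studies.

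**Working it through.** The plan states no CV, agreement share or sample-size figure, so there is nothing to reproduce. The check compares the visit texts and then shows what an assumed effect would do.

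**Step 1. Conditions side by side.**

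| Item | Visit 1 | Visit 2 | Secured as equal? |
|---|---|---|---|
| Feeding before MRI | No step in 8.1, direct imaging allowed; preference in 9.3.1.2 | Firm step in 8.2; preference in 9.3.1.2 | No |
| Other infant measurements | Weight, length, PEA POD, DXA | Weight, length | No |
| Order | Infant-led | Infant-led | Same rule, but PEA POD and DXA can precede only the Visit 1 scan |
| Undressing, diaper change, swaddling for MRI (9.3.1.2) | One instruction | Same instruction | Yes |
| Weighing undressed (9.1) | Yes | Yes | Yes |
| Asleep during MRI (8.1, 8.2) | Yes | Yes | Yes |

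The gap is confined to feeding and to the procedures that may precede the scan.

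**Step 2. Where an effect would go.** Section 11.2 defines % BAT as BAT mass B (MRI) over fat mass F (DXA). Table 1 schedules DXA at Visit 1 only. Assuming that one F serves both visits, it cancels from each infant's relative difference: (B2/F − B1/F) ÷ mean(B1/F, B2/F) = (B2 − B1) ÷ mean(B1, B2). Any change in the MRI value passes in full into the CV and the agreement shares.

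**Step 3. Illustration.** Let c be the true within-infant CV, d a preparation shift, and p the share of infants affected. All three are assumptions. The relative difference D is Normal with variance 2c², and with mean d in affected infants and 0 in the others. The plan gives no CV formula, so I take the root-mean-square paired CV without subtracting the mean visit difference:

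- apparent CV = √(c² + p·d²/2)
- share within t, for a given mean m: Φ((t − m)/(c√2)) − Φ((−t − m)/(c√2)), averaged over affected and unaffected infants

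For example, c = 5%, d = 10%, p = 0.5 gives √(0.0025 + 0.5 × 0.01/2) = √0.005 = 7.1%.

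| True CV | Shift | Affected | Apparent CV | Within 5 / 10 / 15% |
|---|---|---|---|---|
| 3% | 0 | – | 3.0% | 76 / 98 / 100% |
| 3% | 5% | half | 3.9% | 63 / 93 / 100% |
| 3% | 5% | all | 4.6% | 49 / 88 / 99% |
| 3% | 10% | half | 5.8% | 44 / 74 / 94% |
| 3% | 10% | all | 7.7% | 12 / 50 / 88% |
| 5% | 0 | – | 5.0% | 52 / 84 / 97% |
| 5% | 5% | half | 5.6% | 47 / 79 / 94% |
| 5% | 5% | all | 6.1% | 42 / 74 / 92% |
| 5% | 10% | half | 7.1% | 37 / 67 / 86% |
| 5% | 10% | all | 8.7% | 22 / 50 / 76% |
| 10% | 0 | – | 10.0% | 28 / 52 / 71% |
| 10% | 5% | half | 10.3% | 27 / 51 / 70% |
| 10% | 5% | all | 10.6% | 26 / 49 / 68% |
| 10% | 10% | half | 11.2% | 25 / 47 / 66% |
| 10% | 10% | all | 12.2% | 22 / 42 / 60% |

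**Step 4. Could ten pairs reveal it?** Section 4 allows up to 10 infants. At c = 5% with no shift, the 95% half-width for the mean visit difference is t(0.975, 9) × √2 × c/√10 = 2.262 × 1.414 × 5%/3.162 = 5.1%. At c = 3% and 10% it is 3.0% and 10.1%. The 95% interval for a CV from 10 pairs runs from √(10/20.48) = 0.70 to √(10/3.247) = 1.75 times the estimate. A modest shift would be hard to detect from the scan values alone.

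**The case against.** The strongest reply is that the protocol permits a difference but does not prescribe one. The direct-to-imaging route is an example for an infant who arrives asleep, and Section 9.3.1.2 prefers feeding at every scan, Visit 1 included. The two routes also partly exclude each other, since an infant taken straight to imaging has not yet had the PEA POD test. This stands, and it rules out several stronger readings:

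- A reader might infer that infants are undressed differently for the two scans. They are not: one MRI instruction covers both visits, and weighing is undressed at both. Only the extra PEA POD and DXA exposure differs, and it may follow the scan.
- A reader might infer that conditions differ systematically and push the result one way. The documents give no direction, and a shift in every infant is the extreme case.
- A reader might take the background on heat production, cold activation and nutrient uptake (Section 3) as evidence of an effect. That material concerns BAT activity, whereas the numerator here is BAT mass by MRI. Section 9.3.1.1 mentions fat fraction in cited work, but nothing says that a feed or brief exposure alters measured mass.
- A reader might infer that illness between visits goes unrecorded. The questionnaire is at Visit 1 only, but Section 10.2 collects adverse events until the final visit.

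The scan forms are not among the documents either, so the absence of logging is known only from the protocol text. Finally, this is a small pilot in which feasibility matters, and reproducibility under infant-led conditions is a defensible quantity for sizing later studies. It is not, however, what Section 11.2 describes.

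**Conclusion.** The point holds in a limited form. Section 11.2 asserts equal conditions, while 8.1, 8.2 and 9.3.1.2 give one feeding instruction at three different strengths and Visit 1 has two measurements that Visit 2 lacks. The CV and agreement shares may therefore include a preparation component, tied to visit and confounded with growth.

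Its size is unknown. At an assumed true CV of 5%, an assumed shift of 5% to 10% would raise the apparent CV to between 5.6% and 8.7%, depending on whether half or all infants are affected. At a true CV of 10% the same shifts give 10.3% to 12.2%, so the effect matters little when it is small against the true CV. The figures also rest on normal differences and on a CV that does not remove the mean visit difference. They do not show that the precision estimate will be wrong, only that the plan as written could not say what it measures.

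**What to change.** - **Protocol text.** Reconcile 8.1, 8.2, 9.3.1.2 and 11.2 so that one pre-MRI preparation applies at both visits. Which preparation is for the sponsor to choose. Keep the infant-led exception, but log each use.
- **Order.** Where the infant allows, do the Visit 1 MRI before both Visit 1-only measurements. Moving it ahead of PEA POD alone would still leave DXA possible before the scan.
- **Scan record.** At each MRI, record time since last feed and the procedures already done.
- **Analysis (11.2).** Report the mean Visit 2 minus Visit 1 difference with its 95% confidence interval beside the CV, and list which pairs were scanned under matched preparation. With at most 10 pairs the list is descriptive. The mean difference will not by itself separate preparation from growth.
- **If preparation cannot be aligned.** Replace the statement of equal conditions with the actual conditions, and call the CV between-visit reproducibility.

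The cost is a wording change, a few form fields and slightly less flexibility at Visit 1. No visit, scan or infant is added.

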### **12. SUBJECT PAYMENT**

Participants will receive up to \$100 for participation in the study to help offset transportation costs and their time. Participants will receive \$50 for completing the Visit 1 testing and \$50 for completing the Visit 2 testing. One check will be requested at the conclusion of the study. If a participant completes Visit 1 testing but does not complete Visit 2 testing, one check of \$50 for completing the Visit 1 testing will be requested. Checks will be requested from the Pennington Biomedical (LSU) payroll department. If the parent/legal guardian reports that the infant participant has a social security number at the time of the study visit, the infant social security number will be obtained for check processing, and the infant participant will be paid. If the parent/legal guardian reports that the infant participant has not yet obtained a social security number at the time of the study visit which is likely for infants of this age, the parent/legal guardian of the infant participant will be allowed to receive payment on behalf of the infant participant only if the parent/legal guardian agrees to provide his or her own social security number as it is required for check processing.

